
14 Appendices

14.1 Appendix 1: List of prohibited concomitant medications and concomitant medications requiring caution for LDK378

Table 14-1 Prohibited medications that are strong inducers or inhibitors of CYP3A, or CYP3A substrates with narrow therapeutic index, or sensitive CYP2C substrates with narrow therapeutic index**

CYP2C9 substrates with narrow therapeutic index			
warfarin	Phenytoin		
CYP3A4/5 substrates with narrow therapeutic index			
astemizole*	diergotamine	pimozide	alfentanil
cisapride*	ergotamine	quinidine*	terfenadine*
cyclosporine	Fentanyl	tacrolimus	sirolimus
Strong CYP3A4/5 inhibitors			
Macrolide antibiotics:	Antivirals:	Antifungals:	Others:
clarithromycin	Indinavir	itraconazole	conivaptan
telithromycin	Lopinavir	ketoconazole	elvitegravir
troleandomycin	Nelfinavir	posaconazole	mibefradil
	Ritonavir	voriconazole	nefazodone
	saquinavir		
	Tipranavir		
Strong CYP3A/5 inducers			
avasimibe	carbamazepine	phenobarbital	phenytoin
rifabutin	Rifampin	St. John's wort	

* Compounds with risk of QT prolongation

For an updated list of CYP2C substrates, CYP3A substrates, inhibitors and inducers, please reference the Novartis Oncology Clinical Pharmacology internal memo: drug-drug interactions (DDI) database, Oct 2010, which is compiled primarily from the FDA's "Guidance for Industry, Drug Interaction Studies", the Indiana University School of Medicine's Drug Interactions Database, and the University of Washington's Drug Interaction Database.

**Sensitive substrates: Drugs that exhibit an AUC ratio (AUCi/AUC) of 5-fold or more when co-administered with a known potent inhibitor.

Substrates with narrow therapeutic index (NTI): Drugs whose exposure-response indicates that increases in their exposure levels by the concomitant use of potent inhibitors may lead to serious safety concerns (e.g., Torsades de Pointes).

Table 14-2 List of medications to be used with caution

CYP2C9 substrates			
losartan	Irbesartan	diclofenac	ibuprofen
piroxicam	tolbutamide	glipizide	acenocoumarol
celecoxib	sulfamethoxazole	tolbutamide	torsemide
CYP3A4/5 substrates			
dronedarone	capravirine	aripiprazole	simvastatin
alprazolam	Ritonavir	haloperidol	quinine
diazepam	Telaprevir	imatinib	tamoxifen
amlodipine	atorvastatin	nilotinib	tolvaptan
diltiazem	everolimus	methadone	trazodone
nifedipine		boceprevir	vincristine
nisoldipine	erythromycin	brecanavir	verapamil
nitrendipine			
Moderate CYP3A4/5 inhibitors			
ciprofloxacin	Darunavir	grapefruit juice	dronedarone
erythromycin	fosamprenavir	aprepitant	tofisopam
amprenavir	Diltiazem	casopitant	
atazanavir	Verapamil	cimetidine	
Moderate CYP3A4/5 inducers			
bosentan	Efavirenz	etravirine	modafinil
naftillin	Ritonavir	talviraline	tipranavir
Proton pump inhibitors			
esomeprazole	lansoprazole	omeprazole	pantoprazole
rabeprazole			

The list of CYP2C9 and 3A4/5 substrates, 3A4/5 inhibitors and inducers is from the Novartis Oncology Clinical Pharmacology internal memo: drug-drug interactions (DDI) database, Oct 2010, which is compiled primarily from the Indiana University School of Medicine's "Clinically Relevant" Table (<http://medicine.iupui.edu/flockhart/table.htm>), the University of Washington's Drug Interaction Database (druginteractioninfo.org), and the FDA's "Guidance for Industry, Drug Interaction Studies".

Table 14-3 List of prohibited enzyme-inducing anti-epileptic drugs

Prohibited enzyme-inducing anti-epileptic drugs			
carbamazepine	Ethotoin	felbamate	fosphenytoin
phenobarbital	Phenytoin	primidone	topiramate

Table 14-4 List of prohibited QT prolonging drugs

Prohibited medications causing QTc prolongation			
Antiarrhythmic:	Anticancer:	Antibiotic:	Antiangular:
amiodarone	arsenic trioxide	azithromycin	bepridil
disopyramide	vandetanib	clarithromycin*	Antipsychotic:
dofetilide	Antihistamine:	erythromycin*	chlorpromazine
flecainide	astemizole*	moxifloxacin	haloperidol*
ibutilide	terfenadine*	sparfloxacin	mesoridazine
procainamide	Antimalarial:	Antinausea:	pimozide
quinidine*	chloroquine	domperidone	thioridazine
sotalol	halofantrine	droperidol	Opiate agonist:
Antilipemic:	Anti-infective:	GI stimulant:	levomethadyl
probucol	pentamidine	cisapride*	methadone
Antidepressant:			
citalopram			

Please note: *CYP3A substrate

Source: Arizona Center for Education and Research on Therapeutics (CERT), Drugs that prolong the QT interval and/or induce Torsades de Pointes, <http://azcert.org/medical-pros/drug-lists/drug-lists.cfm>

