6.3.1.3 Drugs that are metabolized by CYP450 enzymes

In vitro drug metabolism studies show that the metabolism of LDK378 is mediated by CYP3A4/5. LDK378 is a time-dependent CYP3A4/5 inhibitor and is also a potent reversible inhibitor of CYP2A6, 2E1, 2C9 and 3A4/5 and may consequently increase exposure to drugs metabolized by these enzymes at clinically relevant concentrations. Clinical studies have not yet been performed to confirm the potential effect of LDK378 on substrate drugs metabolized by these enzymes in patients. The risk for CYP2A6 and CYP2E1 is largely mitigated by the low potential for drugs metabolized by these enzymes to be co-administered with LDK378.

Concomitant treatment of LDK378 with weak inhibitors or inducers of CYP3A4/5 is permitted. Caution is advised when LDK378 is co-administered with drugs that are moderate inhibitors or inducers of CYP3A4/5 ([Table 14-2 of Appendix 1](#)). Duration of concomitant

treatment should be kept as short as possible (e.g. less than 1 week), or completely avoided whenever possible. Patients receiving such medications must be monitored closely for any potentiation of toxicity or decrease of clinical benefit due to any individual concomitant medications, and may require dose titration or adjustment. Note that co-administration of LDK378 with strong inhibitors or inducers of CYP3A4/5 is prohibited (refer to [Section 6.3.2.5](#)).

Concomitant treatment of LDK378 with medications known to be metabolized by CYP2C9, and CYP3A4 is allowed with caution ([Table 14-2 of Appendix 1](#)), except for drugs which have narrow therapeutic index/sensitive substrates for these CYP isoforms ([Table 14-1 of Appendix 1](#)).

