6.3.2.8 Herbal medications

Herbal preparations/medications are not allowed throughout the study, as a potential drug-drug interaction is always possible. These herbal medications include, but are not limited to: St. John's wort, Kava, ephedra (ma huang), gingko biloba, dehydroepiandrosterone (DHEA), yohimbe, saw palmetto, and ginseng.

Patients should stop using herbal medications at least 7 days prior to first dose of study treatment.

6.3.2.9 Medications that may prolong the QT interval or have a known risk of inducing Torsades de Pointes

LDK378 has potent activity on the hERG channel with an IC_{50} of 0.4 μ M. However, there were no LDK378-related effects *in vivo* in monkeys at doses as high as 100 mg/kg (human equivalent dose [HED] of 1950 mg). Serial ECGs were collected following a single dose and at steady-state to evaluate the effect of LDK378 on the QT interval in an open-label, dose-escalation, and expansion study ([\[CLDK378X2101\]](#)). A total of 304 patients were treated with LDK 378 doses ranging from 50 to 750 mg with 255 patients treated with LDK378 750 mg. One of 304 patients (<1%) was found to have a QTc >500 msec and 10 patients (3.3%) had an increase from baseline QTc >60 msec. At average steady-state concentrations the upper bound of the 2-sided 90% CI for QTc change from baseline was 16 msec at LDK 378 750 mg. A pharmacokinetic/pharmacodynamic analysis suggested concentration-dependent QTc interval prolongation.

Concomitant administration of LDK378 with drugs known to have a high risk of increasing the QTc interval, and drugs known to increase the QTc interval that are also primarily metabolized by CYP3A4/5 should be avoided. Concomitant use of LDK378 and any medication included in [Table 14-1 of Appendix 1](#) titled "List of prohibited QT prolonging drugs" (i.e., drugs that are generally accepted by the Qtdrugs.org Advisory Board of the Arizona CERT to have a known risk of causing Torsades de Pointes) is not permitted.

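### Erythromycin, haloperidol and methadone are listed both as usable with caution (Table 14-2) and as prohibited QT-prolonging drugs (Table 14-4), and the section imposing the ban cites the wrong table

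*Protocol*

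**What the plan says.** Appendix 1 (protocol section 14.1) sorts concomitant drugs into lists. Two of them matter here: "Table 14-2 List of medications to be used with caution" and "Table 14-4 List of prohibited QT prolonging drugs".

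Section 6.3.1.3 relies on Table 14-2 in two places. On substrates, it says that use of "medications known to be metabolized by CYP2C9, and CYP3A4 is allowed with caution", citing Table 14-2, "except for drugs which have narrow therapeutic index/sensitive substrates for these CYP isoforms", citing Table 14-1. On moderate inhibitors and inducers, it says: "Caution is advised when LDK378 is co-administered with drugs that are moderate inhibitors or inducers of CYP3A4/5", again citing Table 14-2.

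Section 6.3.2.9 covers QT-prolonging drugs. It reports that "A pharmacokinetic/pharmacodynamic analysis suggested concentration-dependent QTc interval prolongation". It says that "drugs known to increase the QTc interval that are also primarily metabolized by CYP3A4/5 should be avoided". It then bans a named list: "Concomitant use of LDK378 and any medication included in [Table 14-1 of Appendix 1](#) titled", followed by the title that Appendix 1 gives to Table 14-4.

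**The concern.** Someone at a site who wants to know whether a patient may take erythromycin, haloperidol or methadone will probably look the drug up in Appendix 1. Table 14-2 answers that it may be used with caution. Table 14-4 answers that it may not be used. The reference in 6.3.2.9 that should lead to the QT list points to a different table, and 6.3.1.3 does not mention the QT list.

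The drugs concerned make this more than a clerical matter. In the study summarised in 6.3.2.9, 10 of 304 patients had a QTc increase above 60 msec and one exceeded 500 msec. Section 6.3.1.3 says LDK378 inhibits CYP3A4/5 and may raise exposure to drugs cleared by it, and Table 14-2 classes all three drugs as CYP3A4/5 substrates. Erythromycin is also listed as a moderate inhibitor of the enzyme that clears LDK378. These are combinations on which a site needs one answer.

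**Working it through.** No statistical figure is involved. The check compares the printed lists entry by entry and then follows each cross-reference.

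**1. Size of Table 14-2.** CYP2C9 substrates 12, CYP3A4/5 substrates 28, moderate CYP3A4/5 inhibitors 14, moderate CYP3A4/5 inducers 8, proton pump inhibitors 5. Total: 12 + 28 + 14 + 8 + 5 = 67 printed entries.

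**2. Overlap with Table 14-4 (33 drugs).**

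| Drug | Entries in Table 14-2 | In Table 14-4 | Marked there as a CYP3A substrate | In Table 14-1 |
|---|---|---|---|---|
| Erythromycin | 2 (substrate; moderate inhibitor) | Yes | Yes | No |
| Haloperidol | 1 (substrate) | Yes | Yes | No |
| Methadone | 1 (substrate) | Yes | No | No |

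That is 3 drugs in 2 + 1 + 1 = 4 entries: 3 of the 28 substrates and 1 of the 14 moderate inhibitors. The other three groups do not overlap with Table 14-4. The share of Table 14-2 is 4/67 = 6.0%.

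**3. Where the cross-references lead.**
- *6.3.1.3, substrates.* The permission is tied to Table 14-2 and the only exception to Table 14-1. None of the three drugs is in Table 14-1, so the exception does not reach them by table number.
- *6.3.1.3, moderate inhibitors.* The sentence is tied to Table 14-2 and has no QT exception.
- *6.3.2.9.* The printed number is 14-1. The title given is that of Table 14-4. A reader who follows the number finds strong CYP3A4/5 inhibitors and inducers and narrow-index substrates, and none of the three drugs. A reader who follows the title finds all three.

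So neither section prints the number 14-4.

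**4. Which rule governs.** Section 6.3 makes its general permission subject to the specific prohibitions in 6.3.2. Section 6.3.2.9 identifies the banned list by its title and by definition (drugs with a known torsades risk). Exclusion criterion 9 covers QT-prolonging drugs for the whole study. All three point to the prohibition.

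**The case against.** The strongest reply is that a careful reader is not misled. Only one table bears the title given in 6.3.2.9, it sits in the same short appendix, and section 6.3 already puts prohibitions above permissions. The tables can also be read as sorted by mechanism, with Table 14-2 covering CYP interactions and Table 14-4 covering QT risk; a drug may then appear in both, and the stricter rule applies. For moderate inhibitors, 6.3.1.3 goes on to ask for short use, or avoidance where possible, with close monitoring.

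There are also safeguards. Exclusion criterion 5 bars a screening QTcF above 470 msec. Tables 7-4 and 7-5 schedule triplicate ECGs throughout treatment, and 7.2.2.6.1 requires central reading. Table 6-3 requires the dose to be withheld and concomitant drugs reviewed at grade 3 QTc prolongation. Finally, few patients were still exposed: of 103 treated, 37 remained on LDK378 at 29-Sep-2015, and the documents mention no further planned amendment.

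Most of this stands, and it limits the consequence. It does not remove the error. The intended rule has to be pieced together from several sections, while Table 14-2 gives the opposite answer in one look. ECG monitoring detects prolongation after exposure; it does not prevent the exposure.

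**Conclusion.** The point holds. Three drugs, in 4 of the 67 printed entries of Table 14-2, have conflicting status. The cross-reference that should settle the matter carries the wrong table number, and the exception in 6.3.1.3 omits Table 14-4. The prohibition is meant to govern, so the defect is an instruction that contradicts itself on a safety matter.

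It should be fixed, but the claim is limited. The documents do not show that any patient received one of these drugs with LDK378. No harm or pharmacokinetic effect is shown, and no analysis set, endpoint or estimate is touched. The finding rests only on the tables and sections as printed in the current protocol.

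Two smaller inconsistencies are separate, and the conclusion does not depend on them. Section 6.3.1.6 leaves proton pump inhibitors out of its permission, although it refers on to 6.3.2.7, which allows them with caution. The H2-blocker timing joins its two conditions with *and* in 6.3.1.6 but with *or* in 6.3.2.7.

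**What to change.** In the next written amendment:

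1. Delete four entries from Table 14-2: erythromycin (both), haloperidol and methadone.
2. In 6.3.2.9, change the reference from Table 14-1 to Table 14-4.
3. In 6.3.1.3, add Table 14-4 to the exception, worded so that it covers both the substrate sentence and the moderate-inhibitor sentence.

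Minor, at the same time: state one proton pump inhibitor rule and one H2-blocker timing rule in both 6.3.1.6 and 6.3.2.7. Optional tidying: remove ritonavir (two entries) and tipranavir (one) from Table 14-2, since Table 14-1 already prohibits them as strong CYP3A4/5 inhibitors.

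Under section 12.1 the amendment needs approval by the sponsor, the ethics bodies and, where required, the Health Authorities. Beyond that the cost is a few lines of text: no new data, visits or analyses, and no change to the SAP.

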14.2.1 Introduction

The purpose of this document is to provide the working definitions and rules necessary for a consistent and efficient analysis of efficacy for oncology studies in solid tumors. This document is based on the RECIST criteria for tumor responses (Therasse et al., 2000) and the revised RECIST 1.1 guidelines (Eisenhauer et al., 2009).

The efficacy assessments described in [Section 14.2.2](#) and the definition of best response in [Section 14.2.3.1](#) are based on the RECIST 1.1 criteria but also give more detailed instructions and rules for determination of best response. [Section 14.2.3.2](#) is summarizing the “time to event” variables and rules which are mainly derived from internal discussions and regulatory consultations, as the RECIST criteria do not define these variables in detail. [Section 14.2.4](#) of this guideline describes data handling and programming rules. This section is to be referred to in the RAP (Reporting and Analysis Plan) to provide further details needed for programming.

14.2.2 Efficacy assessments

Tumor evaluations are made based on RECIST criteria (Therasse et al., 2000), New Guidelines to Evaluate the Response to Treatment in Solid Tumors, Journal of National Cancer Institute, Vol. 92; 205-16 and revised RECIST guidelines (version 1.1) (Eisenhauer, et al 2009) European Journal of Cancer; 45:228-247.

14.2.2.1 Definitions

14.2.2.1.1 Disease measurability

In order to evaluate tumors throughout a study, definitions of measurability are required in order to classify lesions appropriately at baseline. In defining measurability, a distinction also needs to be made between nodal lesions (pathological lymph nodes) and non-nodal lesions.

- **Measurable disease** - the presence of at least one measurable nodal or non-nodal lesion. If the measurable disease is restricted to a solitary lesion, its neoplastic nature should be confirmed by cytology/histology.

For patients without measurable disease see [Section 14.2.3.2.8](#).

Measurable lesions (both nodal and non-nodal)

- Measurable non-nodal - As a rule of thumb, the minimum size of a measurable non-nodal target lesion at baseline should be no less than double the slice thickness or 10mm whichever is greater - e.g. the minimum non-nodal lesion size for CT/MRI with 5mm cuts will be 10 mm, for 8 mm contiguous cuts the minimum size will be 16 mm.
- Lytic bone lesions or mixed lytic-blastic lesions with identifiable soft tissue components, that can be evaluated by CT/MRI, can be considered as measurable lesions, if the soft tissue component meets the definition of measurability.
- Measurable nodal lesions (i.e. lymph nodes) - Lymph nodes ≥ 15 mm in short axis can be considered for selection as target lesions. Lymph nodes measuring ≥ 10 mm and < 15 mm are considered non-measurable. Lymph nodes smaller than 10 mm in short axis at baseline, regardless of the slice thickness, are normal and not considered indicative of disease.

- **Cystic lesions:**
 - Lesions that meet the criteria for radiographically defined simple cysts (i.e., spherical structure with a thin, non-irregular, non-nodular and non-enhancing wall, no septations, and low CT density [water-like] content) should not be considered as malignant lesions (neither measurable nor non-measurable) since they are, by definition, simple cysts.
 - 'Cystic lesions' thought to represent cystic metastases can be considered as measurable lesions, if they meet the definition of measurability described above. However, if noncystic lesions are present in the same patient, these are preferred for selection as target lesions.
- Non-measurable lesions - all other lesions are considered non-measurable, including small lesions (e.g. longest diameter <10 mm with CT/MRI or pathological lymph nodes with \geq 10 to < 15 mm short axis), as well as truly non-measurable lesions e.g., blastic bone lesions, leptomeningeal disease, ascites, pleural/pericardial effusion, inflammatory breast disease, lymphangitis cutis/pulmonis, abdominal masses/abdominal organomegaly identified by physical exam that is not measurable by reproducible imaging techniques.

14.2.2.1.2 Eligibility based on measurable disease

If no measurable lesions are identified at baseline, the patient may be allowed to enter the study in some situations (e.g. in Phase III studies where PFS is the primary endpoint). However, it is recommended that patients be excluded from trials where the main focus is on the Overall Response Rate (ORR). Guidance on how patients with just non-measurable disease at baseline will be evaluated for response and also handled in the statistical analyses is given in [Section 14.2.3.2.8](#).

14.2.2.2 Methods of tumor measurement - general guidelines

In this document, the term "contrast" refers to intravenous (i.v) contrast.

The following considerations are to be made when evaluating the tumor:

- All measurements should be taken and recorded in metric notation (mm), using a ruler or calipers. All baseline evaluations should be performed as closely as possible to the beginning of treatment and never more than 4 weeks before the beginning of the treatment.
- Imaging-based evaluation is preferred to evaluation by clinical examination when both methods have been used to assess the antitumor effect of a treatment.
- For optimal evaluation of patients, the same methods of assessment and technique should be used to characterize each identified and reported lesion at baseline and during follow-up. Contrast-enhanced CT of chest, abdomen and pelvis should preferably be performed using a 5 mm slice thickness with a contiguous reconstruction algorithm. CT/MRI scan slice thickness should not exceed 8 mm cuts using a contiguous reconstruction algorithm. If, at baseline, a patient is known to have a medical contraindication to CT contrast or develops a contraindication during the trial, the following change in imaging modality will be accepted for follow up: a non-contrast CT of chest (MRI not recommended due to respiratory artifacts) plus contrast-enhanced MRI of abdomen and pelvis.

- A change in methodology can be defined as either a change in contrast use (e.g. keeping the same technique, like CT, but switching from with to without contrast use or vice-versa, regardless of the justification for the change) or a change in technique (e.g. from CT to MRI, or vice-versa), or a change in any other imaging modality. A change in methodology will result by default in a UNK overall lesion response assessment. However, another response assessment than the Novartis calculated UNK response may be accepted from the investigator or the central blinded reviewer if a definitive response assessment can be justified, based on the available information.
- **FDG-PET:** can complement CT scans in assessing progression (particularly possible for 'new' disease). New lesions on the basis of FDG-PET imaging can be identified according to the following algorithm:
 - Negative FDG-PET at baseline, with a positive FDG-PET at follow-up is a sign of PD based on a new lesion.
 - No FDG-PET at baseline with a positive FDG-PET at follow-up:
 - If the positive FDG-PET at follow-up corresponds to a new site of disease confirmed by CT, this is PD.
 - If the positive FDG-PET at follow-up is not confirmed as a new site of disease on CT, additional follow-up CT are needed to determine if there is truly progression occurring at that Site (if so, the date of PD will be the date of the initial abnormal CT scan).
 - If the positive FDG-PET at follow-up corresponds to a pre-existing site of disease on CT that is not progressing on the basis of the anatomic images, this is not PD.
- **Chest x-ray:** Lesions on chest x-ray are acceptable as measurable lesions when they are clearly defined and surrounded by aerated lung. However, CT is preferable.
- **Ultrasound:** When the primary endpoint of the study is objective response evaluation, ultrasound (US) should not be used to measure tumor lesions. It is, however, a possible alternative to clinical measurements of superficial palpable lymph nodes, subcutaneous lesions and thyroid nodules. US might also be useful to confirm the complete disappearance of superficial lesions usually assessed by clinical examination.
- **Endoscopy and laparoscopy:** The utilization of endoscopy and laparoscopy for objective tumor evaluation has not yet been fully and widely validated. Their uses in this specific context require sophisticated equipment and a high level of expertise that may only be available in some centers. Therefore, the utilization of such techniques for objective tumor response should be restricted to validation purposes in specialized centers. However, such techniques can be useful in confirming complete pathological response when biopsies are obtained.
- **Tumor markers:** Tumor markers alone cannot be used to assess response. However, some disease specific and more validated tumor markers (e.g. CA-125 for ovarian cancer, PSA for prostate cancer, alpha-FP, LDH and Beta-hCG for testicular cancer) can be integrated as non-target disease. If markers are initially above the upper normal limit they must normalize for a patient to be considered in complete clinical response when all lesions have disappeared.

- **Cytology and histology:** Cytology and histology can be used to differentiate between PR and CR in rare cases (i.e., after treatment to differentiate between residual benign lesions and residual malignant lesions in tumor types such as germ cell tumors). Cytologic confirmation of neoplastic nature of any effusion that appears or worsens during treatment is required when the measurable tumor has met the criteria for response or stable disease. Under such circumstances, the cytologic examination of the fluid collected will permit differentiation between response and stable disease (an effusion may be a side effect of the treatment) or progressive disease (if the neoplastic origin of the fluid is confirmed).
- **Clinical examination:** Clinical lesions will only be considered measurable when they are superficial (i.e., skin nodules and palpable lymph nodes). For the case of skin lesions, documentation by color photography, including a ruler to estimate the size of the lesion, is recommended.

